5.1 Key Safety Variables

The safety of the Test and Control solutions will be determined by the following parameters:

- The primary safety endpoint will be the proportion of eyes with any slit-lamp findings greater than grade 2 over all follow-up visits.
- Adverse Events will also be evaluated. Information regarding any subject- or Investigator- reported AEs will be obtained at each follow-up visit. The rate of adverse events is not a primary endpoint and is not associated with a predefined success criterion.

5.2 **Primary Effectiveness Variables**

The effectiveness of the Test and Control solutions will be determined by the following parameters:

- Overall comfort averaged over all scheduled follow-up visits
- Vision averaged over all scheduled follow-up visits
- The proportion of eyes with a maximum degree of front surface deposits grade of ≤ 2 over all scheduled follow-up visits.

5.3 Risk Assessment and Mitigation

Laboratory, pre-clinical studies and a preliminary clinical study have evaluated BL3100-NBR03 multi-purpose disinfection solution and/or its components. The results support the safety of the formulation for the further evaluation for the proposed use.

The clinical procedures required in Protocol 914 are routinely performed and are standard of care for contact lens wearers. The subjects will be informed of any potential study specific risks in the ICF or if new risks become apparent during the study. Upon review of the clinical and preclinical data no additional risks were identified over the standard contact lens and care solution use. Risk mitigation includes periodic assessments of ocular health by vision care specialists throughout the study, oversight by the study Sponsor, its representatives and the Medical Monitor, and well-defined procedures for the management of adverse events, should they occur.

Anticipated serious adverse device effects are presented in Section 7.1.4.1. Additional descriptions of the risks and benefits to subject safety associated with wearing contact

lenses, use of the contact lens care products, use of the investigational test articles is presented in the BL-3100-NBR03 multi-purpose solution Investigator's Brochure.

6.0 STUDY METHODS

6.1 Study Visits

Refer to Appendix A for a Schedule of Visits and Parameters and Appendix B for Methods of Clinical Evaluation.

Prior to enrollment into the study, the Investigator (or designee) will explain the purpose of the study, procedures, risks/benefits, and subject responsibilities to the potential participant. The subject's willingness and ability to meet the follow-up requirements of the study will be determined. If the subject chooses to participate in the investigation, written ICF, including HIPAA, will be obtained. The subject and the person obtaining written consent will sign and date the IRB-approved ICF. The Investigator should retain the signed original document in the subject's record and provide a copy to the subject. In addition, the applicable privacy regulation requirements must be met.

Eligible subjects will be required to complete and initial the subject-completed forms while at the visits listed below. The data will then be transcribed into electronic Case Report Forms (eCRFs) by qualified site personnel. The original subject-completed forms will be retained by the site in the study files.

Visit Name	Subject-Completed Forms	
Screening/Dispensing Visit	 Informed Consent Initial Lens Performance (Worn Lenses Lens Performance) Lens Performance (Abbreviated Study Lenses Lens Performance) 	
2-Week Follow-up Visit	Lens Performance (Study Lenses Lens Performance)	
1-Month Follow-up Visit	Lens Performance (Study Lenses Lens Performance)	
2-Month Follow-up Visit	Lens Performance (Study Lenses Lens Performance)	
3-Month Follow-up Visit	Lens Performance (Study Lenses Lens Performance)	
Unscheduled Visit(s)	Lens Performance (Study Lenses Lens Performance)	

6.1.1 Screening/Dispensing Visit

After obtaining written informed consent, prospective subjects will be screened to determine whether they meet the entry criteria for the study.

The Screening/Dispensing Visit will proceed as follows:

- a. Collect demographic information as required by the RTSM system
- b. Collect the following baseline lens/lens care history information and lens wear parameters from the subject:
 - Average daily wearing time
 - Hours lenses worn on the day of this visit

- Average hours per day of comfortable wear
- Current lens brand, sphere power and base curve
- Current lens care products
- c. For females of child-bearing potential, inform the potential subject they must use an effective method for birth control during the study and for 2 weeks following the last visit, in a manner that risk of contraceptive failure is minimized. Abstinence is allowed as a birth control method.
- d. Perform the following baseline assessments (without lenses; remove the lenses if the subject wore lenses to the visit):

NOTE: All VA measurements MUST be made using a phoropter.

- Spherocylindrical refraction
- High contrast spectacle-corrected visual acuity (BSCVA)
- Keratometry
- e. Perform a slit-lamp examination (remove the lenses if the subject wore lenses to the visit). Record and sketch any scars and slit-lamp findings greater than Grade 2 in the subject's source document.
- f. If the subject continues to be eligible, have the subject complete and initial the following form:
 - The Initial Lens Performance Assessment Form (Worn Lens Performance Rating Scales), including use of rewetting drops.
- g. Complete the Initial Symptoms/Complaints Form (Worn Lenses Symptoms/Complaints Form).
- h. Dispense three pairs (two for back up only) of the subject's habitual contact lenses. Explain to the subject that the used lenses will be removed at the follow-up visits and returned to the Sponsor.
- i. Instruct subject to insert study lenses

NOTE: wait 2-3 minutes for the new contact lenses to settle on the eye before proceeding

- j. Instruct subject to complete Lens Performance Assessment Form (Abbreviated version: Study Lenses Lens Performance Rating Scale).
- k. Complete the Symptoms/Complaints Form (Study Lenses Symptoms/Complaints).
- 1. Record the following:

- Dispensed lens type (brand), sphere power, base curve
- High contrast distance lens VA
- Over-refraction and distance VA
- Lens wettability
- Lens centration
- Lens movement

- For each eye, compare the distance lens VA to the Distance Best Spectacle-Corrected VA obtained at this visit. If the VA has decreased by 5 letters (0.1 logMAR) or more, provide an explanation.
- If the subject meets all Eligible requirements, log into RTSM system to randomize the subject.
- If the subject is a "Screen Fail", the reason for screen failure must be entered in the RTSM system and maintain a copy of their ICF.
- m. Following randomization, designated study site staff should dispense one Study Kit to the subject via the RTSM system and record in the subject's individual Product Accountability Log.
- n. The unmasked designee will explain to the subject that:
 - Carton and bottle are NOT to be opened in front of any other site personnel.
 - The subject should retain all study materials and bring these items back to the study site at each visit. Place the cartons containing the multi-purpose solution bottles and contact lens cases into the opaque bag provided and return it to the unmasked designee.
- o. The unmasked Designee can dispense the Other Supplies, as needed by the subject (refer to Section 4.4.3).
- p. Complete the following visit eCRFs:
 - Screening/Dispensing Visit
 - Exit Visit (to be completed if the subject is discontinued after randomization)
 - Collect Adverse Events

6.1.2 2-Week Follow-up Visit

The 2-Week Follow-up Visit will proceed as follows:

- a. Collect the following lens wear parameters from the subject:
 - Average daily wearing time (since last visit)
 - Average hours of comfortable wear (since last visit)
 - Hours lenses worn on the day of this visit
 - Did subject replace their lenses? (If so, when)
- b. Complete the Symptoms/Complaints Form (Study Symptoms/Complaints Rating Scales).
- c. Have the subject complete and initial the Lens Performance Assessment Form (Study Lenses Performance Rating Scales, including use of rewetting drops.)
- d. Collect any relevant medical treatment information, including any adverse events, including whether a culture may have been taken.
- e. If the subject did not come to the visit wearing one or more study lenses, go to Step f (below, slit-lamp assessment). Otherwise, evaluate the lenses (while on eye) and record the following assessments:

NOTE: All VA measurements MUST be made using a phoropter.

- High contrast distance lens VA

- For each eye, compare the distance lens VA to the distance lens VA obtained at the Screening / Dispensing visit. If the VA has decreased by 10 letters (0.2 logMAR) or more, provide an explanation.
- Over-refraction and distance VA
- Lens wettability
- Lens deposits (type, percent and degree)
- Lens centration
- Lens movement
- f. Perform a slit-lamp examination (remove and store the lenses if the subject wore lenses to the visit). A lens case must be filled with *Bausch + Lomb Sensitive Eyes*[®] *Saline Solution* (NOT dispensed study solution) for storage of subject's lenses during the exam. If a corneal infiltrate is noted record details according to Corneal Infiltrates, Section 2.0: Slit-Lamp Examination of Appendix B: Methods of Clinical Evaluation.
- g. Record and sketch any scars and slit-lamp findings greater than Grade 2 in the subject's source document.
- h. Return the lenses to the subject to wear until the next study visit.
- i. If an unscheduled lens replacement is required, dispense a new pair of the subject's habitual contact lenses and go to Unscheduled Visits Section 6.1.6.
- j. Complete the following visit eCRFs:
 - 2-Week Follow-up Visit
 - Exit Visit (to be completed if the subject is discontinued or exited at this visit)
 - Collect Adverse Events

6.1.3 1-Month and 2-Month Follow-up Visits

The 1-Month and 2-Month Follow-up Visits will proceed as follows:

- a. If a subject misses either the 1-Month or 2-Month scheduled follow-up visit and cannot be seen prior to the start of the visit window for the next scheduled follow-up visit, then the visit is considered missed.
- b. Collect the following lens wear parameters from the subject:
 - Average daily wearing time (since last visit)
 - Average hours of comfortable wear (since last visit)
 - Hours lenses worn on the day of this visit
 - Did subject replace their lenses? (If so, when)
- c. Complete the Symptoms/Complaints Form (Study Lenses Symptoms/Complaints Rating Scales)
- d. Have the subject complete and initial the Lens Performance Assessment Form. (Study Lenses Performance Rating Scales, including use of rewetting drops.)
- e. Collect any relevant medical treatment information including any adverse events, including whether a culture may have been taken.

f. If the subject did not come to the visit wearing one or more study lenses, go to Step g. Otherwise, evaluate the lenses (while on eye):

NOTE: *All VA measurements MUST be made using a phoropter.*

- distance lens VA
- For each eye, compare the distance lens VA obtained at the Screening / Dispensing visit with the distance lens VA obtained at this visit. If the VA has decreased by 10 letters (0.2 logMAR) or more, provide an explanation.
- Over-refraction and distance VA
- Lens wettability
- Lens deposits (type, percent, and degree)
- Lens centration
- Lens movement
- g. Perform a slit-lamp examination (remove the lenses if the subject wore lenses to the visit). Record and sketch any scars and slit-lamp findings greater than Grade 2 in the subject's source document. If a corneal infiltrate is noted record details according to Corneal Infiltrates, Section 2.0: Slit-Lamp Examination of Appendix B: Methods of Clinical Evaluation.
- h. Unmasked designee to collect the worn lenses from the subject. All worn lenses will be returned to the Sponsor in lens cases filled with Bausch + Lomb Sensitive Eyes® *Saline Solution* at the end of the study. Place the lens case in a labeled zippered bag.
- i. Unmasked designee to collect used Study Kit (bottle and carton) dispensed at the subject's previous visit.
- j. Unmasked designee to place the lens case in the labeled zippered bag and the used Study Kit (bottle and carton) in subject's bag. DO NOT seal subject bags until there is a full accountability by a Clinical Monitor at the end of the study.
- k. Dispense a new pair of subject's habitual lenses, instruct the subject to insert the lenses, and record the following information:

- Dispensed lens type (brand), sphere power, base curve
- distance lens VA
- For each eye, compare the distance lens VA obtained at the Screening / Dispensing visit with the distance lens VA obtained at this visit. If the VA has decreased by 10 letters (0.2 logMAR) or more, provide an explanation
- Over-refraction and distance VA
- Lens wettability
- Lens centration
- Lens movement
- 1. Unmasked designee to dispense a new Study Kit through the RTSM system, and record in the subject's individual Product Accountability Log. If needed, dispense any other supplies.
- m. Complete the following visit eCRFs:
 - 1-Month or 2-Month Follow-Up Visit

- Exit Visit (to be completed if subject is discontinued at this visit)
- Collect Adverse Events

6.1.4 **3-Month Follow-up**

The 3-Month Follow-up will proceed as follows:

NOTE: All VA measurements MUST be made using a phoropter.

- a. Collect the following lens wear parameters from the subject:
 - Average daily wearing time (since last visit)
 - Average hours of comfortable wear (since last visit)
 - Hours lenses worn on the day of this visit
 - Did subject replace their lenses? (If so, when)
 - Last date that lenses were worn after cleaning and storing them in study solution
 - Number of days on study that the subject did not wear the study lenses
 - Percentage of days on study that the subject used study solution and wore their lenses on average (less than 80% = fewer than four out of five days, or 80% or more = at least four out of five days)
- b. Complete the Symptoms/Complaints Form (Study Lenses Symptoms/Complaints Rating Scales).
- c. Have the subject complete Lens Performance Assessment Form (Study Lenses Performance Rating Scales), including use of rewetting drops.
- d. Collect any relevant medical treatment information, including any adverse events, including whether a culture may have been taken.
- e. If the subject did not come to the visit wearing one or more study lenses, go to Step g. Otherwise, evaluate the lenses (while on eye):

- High contrast distance lens VA
- For each eye, compare the distance lens VA obtained at the Screening / Dispensing visit with the distance lens VA obtained at this visit. If the VA has decreased by 10 letters (0.2 logMAR) or more, provide an explanation.
- Over-refraction and distance VA
- Lens wettability
- Lens deposits (type, percent, and degree)
- Lens centration
- Lens movement
- f. Perform a slit-lamp examination (remove the lenses if the subject wore lenses to the visit). Record and sketch any scars and slit-lamp findings greater than Grade 2 in the subject's source document. If a corneal infiltrate is noted record details according to Corneal Infiltrates, Section 2.0: Slit-Lamp Examination of Appendix B: Methods of Clinical Evaluation.
- g. Unmasked designee to collect all worn dispensed lenses from the subject. All worn lenses will be returned to the Sponsor in lens cases filled with *Bausch + Lomb Sensitive*

Eyes ® *Saline Solution* at the end of the study. Place the lens case in a labeled zippered bag.

- h. Unmasked designee to collect used Study Kit (carton and bottle) dispensed at the subject's previous visit.
- i. Unmasked Designee to place the lens case in the labeled zippered bag and the used Study Kit (bottle and carton) in the subject's bag. DO NOT seal the subject's bags until a full accountability is performed by a Clinical Monitor at the end of the study.
- j. All study materials (refer to Sections 4.4.2 and 4.4.3) must be returned to the Sponsor at the end of the study.
- k. Complete the following visit eCRFs:
 - 3-Month Follow-up Visit
 - Exit Visit (if there is an ongoing AE at the time of the 3-month visit, do not complete the Exit Visit and follow up via Unscheduled visit (s) instead
 - Collect Adverse Events

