6.1.6 Unscheduled Visits

Additional visits may be scheduled, as necessary, to ensure the safety and well-being of subjects. All additional exams should be fully documented in the source documents and on Unscheduled Visit eCRFs, as appropriate. Refer to Section 7.2 for the procedures required should an AE be present at an Unscheduled visit. Visits intended to fulfill scheduled visit requirements that fall outside the designated scheduled visit range are not Unscheduled Visits. In these cases, the visit data will be collected and transcribed to the appropriate scheduled visit eCRFs.

If a subject is seen for multiple visits during a given visit timeframe, the data from the visit that is intended to meet the protocol requirements for the scheduled visit should be captured on the visit eCRF. Where such a determination cannot be made, the first visit within the scheduled visit interval will be used for completion of the protocol required scheduled visit eCRF. Data from any additional visits within a scheduled visit interval will be captured on an Unscheduled Visit eCRF.

Procedures to be followed during an Unscheduled Visit will depend on the reason for the visit:

- a. Indicate the reason for the Unscheduled Visit.
- b. If the subject is experiencing problems, assessments will be performed according to the Investigator's judgement.
- c. If the exclusive purpose of the visit is to dispense study lens/ Study Kit and the subject is not experiencing any problems (refer to Section 6.1.8.).
- d. Collect the following lens wear parameters from the subject:
 - Average daily wearing time (since last visit)
 - Average hours of comfortable wear (since last visit)
 - Hours lenses worn on the day of this visit
 - Did subject replace their lenses? (If so, when)
- e. Complete the Symptoms/Complaints Form (Study Lenses Symptoms/Complaints), including use of rewetting drops
- f. Have the subject complete and initial the Lens Performance Assessment record (Study Lenses Performance Rating Scales).
- g. Collect any relevant medical treatment information, including any adverse events, including whether a culture may have been taken.
- h. If the subject did not come to the visit wearing one or more study lenses, go to Step i. Otherwise, evaluate the lenses (while on eye):

- High contrast distance lens VA
- Over-refraction and distance VA
- Lens wettability
- Lens deposits (type, percent and degree)
- Lens centration
- Lens movement

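### At the 3-Month visit, Protocol 6.1.4 step e routes subjects who arrive without study lenses past the slit-lamp examination, the last scheduled look at the primary safety endpoint

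*Protocol*

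**What the plan says.** Protocol 6.1.4, 3-Month Follow-up, has three consecutive steps:

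- Step e: "e. If the subject did not come to the visit wearing one or more study lenses, go to Step g". Otherwise the lenses are evaluated on the eye.
- Step f: "f. Perform a slit-lamp examination (remove the lenses if the subject wore lenses to the visit").
- Step g: "g. Unmasked designee to collect all worn dispensed lenses from the subject".

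The other follow-up sections contain the same skip:

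- 6.1.2 (2-Week), step e: "go to Step f (below, slit-lamp assessment").
- 6.1.3 (1-Month and 2-Month), step f: "f. If the subject did not come to the visit wearing one or more study lenses, go to Step g". There, step g reads "g. Perform a slit-lamp examination (remove the lenses if the subject wore lenses to the visit").
- 6.1.6 (Unscheduled), step h: "h. If the subject did not come to the visit wearing one or more study lenses, go to Step i". There, step i is the slit-lamp examination.

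Appendix A places the slit-lamp examination among the procedures done without lenses. It marks it at Screening, at all four scheduled follow-up visits and at Unscheduled visits, and leaves it blank in the Exit column.

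Protocol 8.1.4 defines the primary safety endpoint as the proportion of eyes with any slit-lamp finding above Grade 2 over all follow-up visits. SAP 4.5.1 classifies each eye from its non-missing observations, and SAP 4.1.4 counts unscheduled visits after baseline.

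**The concern.** Read literally, step e lets a subject who comes without lenses leave the 3-Month visit unexamined. An eye with no finding above Grade 2 at any other follow-up visit is then classified as Absent, whatever its state at Month 3.

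Success on this endpoint is required for the trial to succeed (Protocol 8.2). If skipping is equal in the two arms, lost findings lower both observed rates in the same proportion. A true difference at the non-inferiority margin therefore shrinks, which favours a false conclusion of non-inferiority. In a single trial the effect can go either way: losing a Test finding can turn a fail into a pass, and losing a Control finding can turn a pass into a fail.

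Subjects without lenses may also not be a random group. Appendix C tells subjects to discontinue use and consult the investigator if irritation, excessive tearing or impaired vision occurs. This is a plausible mechanism; the documents do not measure it.

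**Working it through.** **1. Where each skip lands**

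| Section | Skip from | Skip to | Step reached |
|---|---|---|---|
| 6.1.2 2-Week | e | f | slit-lamp |
| 6.1.3 1-/2-Month | f | g | slit-lamp |
| 6.1.6 Unscheduled | h | i | slit-lamp |
| 6.1.4 3-Month | e | g | lens collection |

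Only 6.1.4 misses its target. The likely cause is visible in the lettering. Section 6.1.3 opens with a missed-visit step, "a. If a subject misses either the 1-Month or 2-Month scheduled follow-up visit", which 6.1.4 does not have. The letters in 6.1.4 therefore move up by one, but the pointer stayed at g.

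**2. Whether anything else recovers the examination**

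The Exit Visit (6.1.5) calls for an ocular examination but lists refraction, BSCVA and keratometry, not slit-lamp. Protocol 9.4 requires omissions to be explained and all eCRF data to be verified. That should reveal a missed examination but cannot restore it.

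**3. The plan's own power figure**

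Inputs from Protocol 7/8.3.4 and SAP 2.2.4 and 4.5.2.1: 300 eyes per arm, 0.8% in each arm, margin 5%, one-sided 97.5% Newcombe-Wilson upper limit, eyes independent. Success means a limit below 5%, or no findings in either arm.

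Upper limit = (pT − pC) + √[(uT − pT)² + (pC − lC)²], where uT is the Wilson upper limit for Test and lC the Wilson lower limit for Control.

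Summing exact binomial probabilities over all outcomes gives power of 99.94%. The plan states 99%, so its figure is met.

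**4. Findings lost at the planned rate**

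Let s be the share of eyes skipped and f the share of findings seen only at Month 3. Neither is in the documents. I take s = 2–10% and f = 25–50%, with skipping equal in both arms and unrelated to having a finding.

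- Eyes skipped per arm: 300 × 0.02 = 6, to 300 × 0.10 = 30.
- Expected findings lost, upper bound with f = 1: 6 × 0.008 = 0.048, to 30 × 0.008 = 0.24.
- Power with both rates multiplied by (1 − f × s): 99.95–99.96%.

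**5. False success with true rates on the margin**

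Test 5.8%, Control 0.8%, both multiplied by (1 − f × s). For example, f × s = 0.05 gives 5.51% and 0.76%, a difference of 4.75 points.

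| Skipped (s) | f = 25% | f = 50% |
|---|---|---|
| none | 2.25% | 2.25% |
| 2% | 2.34% | 2.43% |
| 5% | 2.47% | 2.72% |
| 10% | 2.72% | 3.29% |

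The risk reaches the nominal 2.5% at f × s = 0.0139. With 340 eyes per arm (all enrolled), it is 2.28% with no skipping, 2.37–2.47% at 2% and 2.78–3.39% at 10%; the threshold is f × s = 0.0115.

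**6. Sensitivity to one eye (300 per arm)**

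- 9 Test v 2 Control: 0.0233 + √[(0.0560 − 0.0300)² + (0.0067 − 0.0018)²] = 4.98%, pass.
- 10 v 2: 5.40%, fail. One lost Test finding turns this into a pass.
- 9 v 1: 5.28%, fail. One lost Control finding turns the 9 v 2 pass into this fail.

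At the planned 0.8% rate, the probability of 9 or more Test eyes with a finding is only 0.08%, so such a close result is unlikely.

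**The case against.** The strongest reply is that the practical weight is slight and partly covered elsewhere.

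- **Sensitivity analyses.** SAP 4.5.3 imputes missing scheduled-visit values under best and worst cases and describes a tipping-point analysis for the slit-lamp endpoint. These would show the effect of skipped examinations but leave the primary result unchanged. They also have a cost: with 2 observed findings per arm, 8 skipped Test eyes (four subjects) imputed as Present give 10 v 2, a worst-case fail caused by avoidable missing data.
- **Symptomatic subjects.** Step d of 6.1.4 collects adverse events before the skip, and an ongoing event leads to Unscheduled visits, where a slit-lamp examination is listed and counts. Assessments there follow the investigator's judgement, so the cover is partial.
- **Site behaviour.** Appendix C tells subjects to wear their lenses to visits, and a site working from Appendix A would examine everyone. Omission is possible, not certain.
- **The numbers.** The false-success figures rest on two assumed ranges and on independent eyes. Relaxing independence matters more: with nothing skipped, an inter-eye correlation of 0.5 (assumed) already puts the risk at the margin at about 5.1%. The shifts in the table are small beside that.
- **Existing output.** SAP 4.9 already plans slit-lamp summaries by visit and listings of all visits, so a listing of missing examinations adds little work and some overlap.

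These points limit the size of the problem. None removes the contradiction between step e and the rest of the protocol.

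**Conclusion.** The concern holds. Step e of 6.1.4 is an operative instruction that conflicts with the next step, with Appendix A and with the parallel sections. If followed, it drops the last scheduled assessment of a co-primary safety endpoint. It reads as a carried-over cross-reference, not a deliberate choice.

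The expected consequence is small: a fraction of one finding per arm at the planned rate and no loss of power. False-success risk at the margin exceeds 2.5% only when the product of the two assumed shares is above about 1.4% (1.2% with 340 eyes per arm). These sizes assume equal skipping in the arms, skipping unrelated to findings, and independent eyes. The loss would be larger if subjects stay out of lenses because of ocular problems. It should be corrected because it affects a primary endpoint and the correction is simple.

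**What to change.** In Protocol 6.1.4 step e, change the destination from step g to step f, in line with Appendix A and sections 6.1.2, 6.1.3 and 6.1.6. This adds no procedure to the protocol's own schedule.

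If 3-Month visits have already occurred, list by arm those with no slit-lamp record, so that the extent and balance of the loss are known. The planned SAP 4.9 listings can supply most of this.

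The edit is one letter, made by amendment or site memo. An amendment needs IRB/EC approval before implementation (Protocol 9.7) and must reach about 22 sites, so the process costs more than the edit.
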